Cover Page for Study Protocol

Sponsor-Investigator:	[name]	
NCT Number:	NCT03505476	
Unique Protocol ID:	201801808	
Official Title:	Optimizing the Previs Device for	
	Prediction of Postoperative Ileus	
Date of Document:	28 September 2020	

Device Name:	Previs Device
Title of Study:	Optimizing the Previs device for Prediction of Postoperative Ileus (Previs Optimization)
Study Center:	University of Iowa
Estimated number of subjects:	475 subjects (50% male, 50% female) will be recruited and enrolled in this study.
Study Period:	February 2018 until completion
Estimated date of first enrollment:	February 2018 will be the earliest day of enrollment, pending approval from UI IRB.
Estimated date of last enrollment:	We estimate that all subjects will be enrolled by January 2020.
Sponsor:	Entac Medical, Inc.
Version:	4.0
Date:	September 28, 2020

Table of Contents

I.	Statement of Compliance:
II.	IRB Oversight:
III.	Location of Study Procedures:
IV.	Trial Design:
V.	Study Aims:
VI.	Main Screening Criteria:
VII.	Screening/Recruitment procedures:
VIII.	Inclusion Criteria:
IX.	Exclusion Criteria:
X.	Study Procedures:
	Table 1. Study Procedures: 10
XI.	Possible Risks of the Study:
XII.	Adverse Event Reporting:
XIII.	Data Management:
XIV.	Primary End points:
XV.	Payment for Participation:
XVI.	Subject Safety:
XVII.	Statistical design plan:

I. Statement of Compliance:

This study will be conducted in compliance with the protocol, Good Clinical Practice and the applicable Food and Drug Administration and other Department of Health and Human Services regulatory requirements.

All key personnel (all individuals responsible for the design and conduct of this study) have completed Human Subjects Protection and Good Clinical Practice training.

II. IRB Oversight:

Human Subjects Office / IRB J. [name] [name] FWA#: FWA00003007 Voice: [contact] [contact] Email: [contact]

III. Location of Study Procedures:

University of Iowa Hospitals and Clinics (UIHC) [name]

IV. Trial Design:

This is a prospective, non-randomized, open label, single center study designed to assess and optimize performance of the Previs device.

V. Study Aims:

The aims of this study are:

1) To incorporate digital signal processing algorithms and design changes from prior trials into a re-designed prototype, self-contained, noninvasive device that retains or improves the predictive accuracy.

2) To continue making iterative refinements on prototype device design to one that reliably performs in a health care environment.

VI. Main Screening Criteria:

We will recruit men and non-pregnant women of any ethnic background between the age ≥ 18 and ≤ 100 years that are scheduled to undergo an elective intestinal resection surgery by the colorectal surgery service at UIHC.

VII. Screening/Recruitment procedures:

Adult patients presenting to the Digestive Health Center at UIHC for elective intestinal resection surgery or to Urology Clinic at UIHC for cystectomy, that qualify, will be offered participation in the trial. Study team will review potential subject's chart for possible inclusion/exclusion criteria. This pre-screening is done so that potential subjects and their families are not approached until the study team reviews and verifies that it would appear that the subject may qualify.

The study team will approach the potential subject and tell them that they may qualify for a study and ask if they are interested in hearing about the study. If the potential subject is interested, the study will be explained to them in detail. They will be encouraged to ask questions and talk it over with the treating physician and family members.

If the potential subject would like to participate, one of the members of the study team will go over the consent form with them, answering any questions they may have as the study team goes through the consent form. Once they have reviewed the entire consent form the study team will ask them once again if they have any questions. After all questions are answered, they can sign the consent form if they choose to participate. The patient will have the time between the discussion of the study and the day of surgery to decide if they would like to participate. This time interval is typically 1 to 2 weeks.

To avoid any coercion all subjects are offered the opportunity to talk with the treating physician or family prior to signing a consent form. Study participation has no influence on the standard of care they would otherwise receive for their disease process

VIII. Inclusion Criteria:

- Age ≥ 18 and ≤ 100 years
- Patient undergoing elective intestinal resection surgery by the colorectal surgery service at UIHC.
- Patient undergoing cystectomy surgery by the urology service at UIHC

IX. Exclusion Criteria:

- Allergies to any of the device components (ie: adhesive)
- Inability to have prototype device applied to their abdominal wall due to a condition (ie: fistulas, stomas, drains, etc).
- Patients who develop documented evidence of intraperitoneal infection or urinary tract infection within 14 days of surgery will be excluded from analysis for primary outcome (but data will undergo analysis for potential detection of secondary ileus)

X. Study Procedures:

- Potential subject is approached at preoperative visit to discuss study, if interested.
- Informed consent signed.
- Previs device is applied either in the operating room at the completion of surgery or in the recovery room.
- Time and serial number of device application will be logged into study register.
- Study team member will administer Instrument Questionnaire daily, while hospitalized, for up to 10 days.
- Study team member will remove the Previs device 10 days post-operative or at subject discharge from the hospital.
- Study team will monitor the medical record and talk with subject for 14 days to collect any data related to a possible infection (intraperitoneal or urinary tract infection).
- Study team member will contact the subject 14 days post-operative to administer Instrument Questionnaire.
- Study team will review the subject's medical record to assess for any evidence of hospital readmission within 30 days of discharge.

Table 1Schedule of events

Event	Screening Visit	Day of Surgery (Day 1)	Day 2,3,4,5,6,7,8,9,10	14 Day Follow-Up
Informed Consent	Х			
Medical History	Х			
Medical Record		X	X	X
Review				
Review of	Х			
inclusion/exclusion				
criteria to confirm				
subject eligibility				
Device placement		X		
Device removal			X ^a	
Instrument		X	X	X
Questionnaire				

Adverse events	Х	Х	Х
monitoring			

a. At day 10 post-operative or discharge, whichever comes first.

XI. Possible Risks of the Study:

Risk of skin irritation where the device is placed. To minimize the risk of skin irritation, subjects will not be enrolled who have allergies to any of the device components or the adhesives that will be used. Study members will also monitor the device placement to ensure there is no irritation.

Loss of confidentiality is also a risk. To reduce risk of a loss of confidentiality, precautions will be taken to ensure privacy. The PI and study team will maintain appropriate medical and research records for this study, in compliance with ICH E6 GCP, Section 4.9 and regulatory and institutional requirements for the protection of confidentiality of subjects. Research records generated in this study will be stored in file cabinets in a locked room and/or on a secure electronic database. Only authorized study team at the sites will have access to the data. Subjects will not be directly identified by name. Any identifiers that would link the subjects to the database will be stored in a password protected RedCap database. All subjects will be identified by a coded ID number.

XII. Adverse Event Reporting:

Subjects are monitored for adverse events during the study. Subjects are also educated on the risks of the study and contact phone numbers for the study team. Subjects are encouraged to contact the study personnel with any questions or concerns.

The University of Iowa requires Investigators to collect and report to the University of Iowa IRB if any of the following occur:

- An unanticipated problem involving risks to subjects or others is any event or problem that:
 - was unexpected (in terms of nature, severity or frequency) given (a) the research procedures that are described in the protocol-related documents, such as the IRB- approved research protocol and informed consent document; and (b) the characteristics of the subject population being studied AND
 - 2) suggests that the research places subjects or others (those not directly involved in the research such as research staff or family members) at a greater risk of harm (including physical, psychological, economic, or social harm) than was previously known or recognized AND
 - 3) is related or possibly related to participation in the research (possibly related means there is a reasonable possibility that the incident, experience or outcome may have been caused by the procedures involved in the research).
- Receipt of new information

During the course of a study, researchers may become aware of new information that would impact a subject's decision to participate, or continue participating in the research study. For example, interim analyses of data may identify a trend which impacts the safety of subjects, or may identify early efficacy (benefit) of one of the interventions under study. In addition, results from other research studies or changes in standards of practice or care may affect conduct of a study and would need to be communicated to research subjects.

• Noncompliance

Noncompliance is a failure to follow the federal regulations with respect to protection of human subjects in research or failure to follow the determinations of the IRB with respect to conduct of the research as approved by the IRB.

Once per year, the IRB is required to review and approve all non-exempt research projects at intervals appropriate to the degree of risk, but not less than once a year. This is called "continuing review." Continuing review for non-exempt research is required to occur as long as the research remains active for long-term follow-up of the research subject, even when the research is permanently closed to the enrollment of new subjects and all subjects have completed all research-related interventions and to occur when the remaining research activities are limited to collection of private identifiable information.

XIII. Data Management:

The following people/agencies may have access to subject data/records:

- Study team
- Federal government regulatory agencies
- Auditing departments of the University of Iowa
- University of Iowa IRB
- Sponsor and/or its representative

To protect confidentiality, we will assign each subject a study ID. All records will be in a locked cabinet in a locked office or password protected computer system. Data and records will be managed as follows:

- Paper/hard copy records (hard copy surveys, questionnaires, case report forms, pictures, etc.) Whenever possible, subject identifying information will be blacked out on all paper or hard copy records and replaced with the subject's unique study identifier. Paper records will be stored in a locked file cabinet in the study team's locked office.
- Electronic records (computer files, electronic databases, etc.) All electronic data bases will only be accessed by the study team and available only with a username and password assigned to study team by the PI.
- After the completion of the study, all identifiable information will be destroyed according to the University of Iowa's IRB standards, as soon as possible.

XIV. Primary End points:

Performance of Previs device within 18 hours after surgery for predicting subsequent development of gastrointestinal impairment due to ileus.

XV. Payment for Participation:

Subjects will not receive payment for participating in this study. The study related device and study procedures will be paid for by the study.

XVI. Subject Safety:

- To minimize risks all subjects are carefully pre-screened and screened trying to identify any factors that could contribute to increased risk.
- All study procedures are completed at University of Iowa Hospitals and Clinics by a very experienced and well trained staff and monitored by the Principal Investigator.
- All confidential information is kept in locked offices and password protected computers only available to study team members.
- The participant has contact information and study team members available 24/7.

XVII. Statistical design plan:

The definition of post-operative ileus is "the presence of emesis, need for nasogastric intubation, or reversal of the diet beyond 24 hours from the completion of surgery". As the goal of the first phase of this trial is to optimize the device for predicting ileus, we will be maximizing the performance of the device through measurement of sensitivity, specificity, positive predictive value, negative predictive value, AUC, and accuracy of the device for each 10-20 patients (dependent upon the incidence of ileus in each group). The device performance will be compared to the surgeon prediction of ileus development, which will be assessed within the first 24 hours after surgery. The threshold for use in the second phase (validation phase) will be chosen to maximize sensitivity while maintaining the highest possible specificity. Ultimately, device performance will be considered successful if sensitivity higher than that of surgeons can be achieved for predicting ileus.

The study team would like to increase our enrollment plan to 225 patients. We believe that there will be a significant need for pre-optimization where the algorithm is tweaked based upon results in smaller cohorts. Enrollment of 225 patients should allow us an adequate number of cohorts to iteratively pre-optimize the algorithm prior to validation in the final cohort.

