Cover Page for Statistical Analysis Plan

Sponsor-Investigator:	[name]
NCT Number:	NCT03505476
Unique Protocol ID:	201801808
Official Title:	Optimizing the Previs Device for Prediction of Postoperative Ileus
Date of Document:	11 December 2018

Statistical Analysis

The definition of post-operative ileus is "the presence of emesis, need for nasogastric intubation, or reversal of the diet beyond 24 hours from the completion of surgery". As the goal of the first phase of this trial is to optimize the device for predicting ileus, we will be maximizing the performance of the device through measurement of sensitivity, specificity, positive predictive value, negative predictive value, AUC, and accuracy of the device for each 10-20 patients (dependent upon the incidence of ileus in each group). The device performance will be compared to the surgeon prediction of ileus development, which will be assessed within the first 24 hours after surgery. The threshold for use in the second phase (validation phase) will be chosen to maximize sensitivity while maintaining the highest possible specificity. Ultimately, device performance will be considered successful if sensitivity higher than that of surgeons can be achieved for predicting ileus.

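### Tuning the algorithm on results from cohorts of 10-20 patients rests on very few ileus cases and is strongly influenced by chance; re-scoring all compatible recordings at each update uses the same patients better

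*Protocol*

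**What the plan says.** Protocol section XVII describes a first phase that optimizes the device and a second that validates it. In the first phase six performance measures are calculated "for each 10-20 patients (dependent upon the incidence of ileus in each group". The closing paragraph explains that "the algorithm is tweaked based upon results in smaller cohorts", and justifies the enrollment figure by the number of cohorts it provides to "iteratively pre-optimize the algorithm prior to validation in the final cohort". The SAP repeats the rule on measurement: "accuracy of the device for each 10-20 patients (dependent upon the incidence of ileus in each group". Success is defined on sensitivity alone: "device performance will be considered successful if sensitivity higher than that of surgeons can be achieved for predicting ileus".

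The documents do not give an expected incidence of ileus, a minimum number of ileus cases before a change is made, a rule for accepting a change, or the set of recordings on which a new version is assessed.

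**The concern.** Sensitivity is estimated only from patients who develop ileus, and the precision of an AUC is limited mainly by the smaller class. A cohort of 10-20 patients contains few ileus cases at any plausible incidence. If the next change to the algorithm depends on such a cohort's figures, a useful change can look harmful and a useless one can look like progress. The stated goal of the first phase is to optimize the device, so what is at stake is the quality of the algorithm that reaches validation and the return on the patients enrolled.

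**Working it through.** The plan gives no inputs from which its 10-20 can be reproduced, so the check asks how much a cohort of that size can show.

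**Inputs**
- Cohort size 10-20: protocol section XVII and SAP.
- Incidence: not stated; 10-30% assumed.
- True AUC 0.80 for the better version and 0.70 for the other: assumed.
- Cumulative set of 150 patients: an illustration within the 225 of section XVII. The cover page gives 475, which should be reconciled separately; this point does not depend on which is right.

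**1. Cases per cohort.** Expected counts run from 10 × 0.10 = 1 to 20 × 0.30 = 6. The realised count varies from 0 to about 9 (5th to 95th percentiles over this range). The chance of no case at all is 0.9^10 = 35% for 10 patients and 0.9^20 = 12% for 20 patients at 10% incidence, and 0.8^10 = 11% for 10 patients at 20%. Sensitivity and AUC are then undefined.

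**2. Precision of the AUC (Hanley-McNeil).** With m cases, n non-cases, a = A/(2 − A) and b = 2A²/(1 + A):

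SE² = [A(1 − A) + (m − 1)(a − A²) + (n − 1)(b − A²)] / (mn)

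For A = 0.80, a − A² = 0.0267 and b − A² = 0.0711.

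| Patients | m, n | SE² | SE |
|---|---|---|---|
| 10, at 10% | 1, 9 | (0.16 + 0 + 0.569)/9 | 0.285 |
| 20, at 30% | 6, 14 | (0.16 + 0.133 + 0.924)/84 | 0.120 |
| 150, at 10% | 15, 135 | (0.16 + 0.373 + 9.529)/2025 | 0.070 |
| 150, at 30% | 45, 105 | (0.16 + 1.173 + 7.396)/4725 | 0.043 |

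The result does not hinge on the assumed incidence. At 50% a cohort has 5-10 expected cases and the SE is still 0.10-0.15.

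**3. Comparing two versions in separate cohorts.** Scores were simulated as normal with unit variance, cases shifted by √2·Φ⁻¹(AUC), that is 1.19 for AUC 0.80 and 0.74 for 0.70. With 2-4 cases per cohort, the 0.80 version looks worse in 31-37% of comparisons, ties counted half. For the largest expected count (6 cases, 14 non-cases) a normal approximation serves. The SE at AUC 0.70 is √[(0.21 + 5 × 0.0485 + 13 × 0.0865)/84] = 0.137, so the SE of the difference is √(0.120² + 0.137²) = 0.182. Then 0.10/0.182 = 0.55, and the better version looks worse in about 29%.

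**4. Comparing them on the same patients.** With 150 patients scored by both versions and a score correlation of 0.5 (assumed), the better version looks worse in about 7% (15 cases, 135 non-cases) and about 2% (30 and 120); repeated runs stay within about 2-8%. Part of the gain comes from numbers alone: in two separate sets of 20 cases and 80 non-cases the figure is 12%, and with 40 and 160 it is 5%.

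**5. The same question for sensitivity.** The exact 95% interval is 9-99% for 2 of 3 cases detected and 36-99.6% for 5 of 6. If sensitivity truly rises from 70% to 80%, the SE of the difference between two cohorts with 6 cases each is √[(0.21 + 0.16)/6] = 0.25, two and a half times the gain. The better version then looks better in 53%, tied in 25% and worse in 23%; with 3 cases each, 42%, 36% and 21% (rounded). Scored on the same 22 cases (about 225 × 10%), with 15% of cases gained and 5% lost, SE = √[(0.20 − 0.10²)/22] = 0.09, and it looks better in 80% and worse in 9%. With 45 cases (225 × 20%) the figures are 92% and 4%.

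**6. Effect on the result of tuning.** In an illustrative simulation (5 features, 220 patients, 600 runs, best attainable AUC 0.777), tuning on the newest group reached a mean true AUC of 0.66-0.72. Tuning on all data to date reached 0.71-0.76. The AUC on the reused data was too high by about 0.015-0.053.

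**The case against.** - **Silence on re-scoring.** A reader might infer that the plan discards earlier recordings and judges each version only on its own cohort. The text does not say so; it says that cohort results drive the changes and leaves re-scoring open. The concern is therefore with a stated basis for tuning that is very imprecise, and with a gap that should be filled.
- **Direction of the error.** A reader might infer that most apparent gains or losses point the wrong way. They do not. With a true AUC difference of 0.10, the better version still wins roughly two thirds of cohort comparisons. With a true 10-point gain in sensitivity, so do about two thirds of the untied ones (42/63 = 67% with 3 cases, 53/76 = 70% with 6). Chance dominates the size of an apparent change, and all of it where two versions do not truly differ.
- **The threshold.** It might be inferred that the validation threshold is set on one small cohort. The documents do not say which patients it is chosen on.
- **Flexible cohort size.** The plan lets the size depend on incidence, but within 10-20, and at 10% incidence a cohort of 20 still has no case 12% of the time.
- **Hardware.** Protocol section V foresees iterative prototype changes, so some recordings may not be comparable, and the documents do not state that raw signals are kept. This stands and limits the pool. Section IX does plan further analysis of data from patients with an infection found up to 14 days after surgery, which suggests that data are retained.
- **Optimism.** Developers who have seen all recordings have in effect used every fold, so cross-validation cannot remove all optimism. This also stands, and is why new cohorts must keep an out-of-sample role.
- **Containment.** Validation takes place in a final cohort, which noisy tuning does not by itself bias. That protects the final estimate, but does not recover a better version passed over by chance.

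**Conclusion.** The concern holds as one of efficiency and of an unspecified update rule. Results from a single cohort of 10-20 are too imprecise to steer the algorithm. The AUC standard error is about 4 times (0.285/0.070, 10 patients at 10%) to 2.8 times (0.120/0.043, 20 patients at 30%) that on 150 patients at the same incidence. A version better by 0.10 in AUC looks worse about a third of the time in separate cohorts with 2-4 cases, against about 2-8% in a paired comparison on 150 patients.

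These sizes rest on assumed incidence (10-30%), assumed AUCs (0.80 and 0.70), normally distributed scores, a score correlation of 0.5, and 150 recordings from compatible hardware; a smaller compatible pool gives a smaller gain. The documents do not support the further inference that the final validation is invalid. The change should be made, because it strengthens the phase whose purpose is optimization.

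**What to change.** Add to the SAP and to protocol section XVII:

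1. At each update, re-score all stored recordings from compatible hardware with the old and the new algorithm version. Base the change on a paired, cross-validated AUC comparison on that cumulative set.
2. Run each newly adopted version on the next cohort first, as an out-of-sample check, and only then add that cohort to the pool.
3. Choose the validation threshold from out-of-fold scores over all compatible optimization patients.
4. Lock algorithm and threshold before the final cohort.
5. State the minimum number of ileus cases required before a change is considered, and the incidence assumed in setting it.

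The cost is wording, computing and retention of raw signals; no patients or procedures are added. There are two limits. Recordings from incompatible prototypes cannot be pooled, so a hardware change may restart the pool. Repeated reuse leaves some optimism, which only new cohorts and the final cohort remove.

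### Success rests on sensitivity alone, with a movable device threshold set against a surgeon prediction of unstated format, so a different cut-off can pass for better prediction

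*Protocol*

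**What the plan says.** Protocol Section XVII and the SAP use the same wording for the comparison.

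- **Device measures.** Six are listed for the optimization phase: "sensitivity, specificity, positive predictive value, negative predictive value, AUC, and accuracy of the device". None is given priority over the others.
- **Comparator.** "The device performance will be compared to the surgeon prediction of ileus development". The only detail about the surgeon's prediction is its timing: "which will be assessed within the first 24 hours after surgery". Neither document gives a response format, and the schedule of events (Protocol Section X, Table 1) has no row for collecting it. Neither says which of the six measures are compared with the surgeon.
- **Device cut-off.** "The threshold for use in the second phase (validation phase) will be chosen to maximize sensitivity while maintaining the highest possible specificity". A chosen threshold implies a graded device output, although no score is described.
- **Success.** "device performance will be considered successful if sensitivity higher than that of surgeons can be achieved for predicting ileus". The rule carries no specificity condition.
- **Primary endpoint.** Protocol Section XIV gives "Performance of Previs device within 18 hours after surgery for predicting subsequent development of gastrointestinal impairment due to ileus" and does not name a performance measure.

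**The concern.** Sensitivity and specificity trade off along a predictor's ROC curve. Lowering the cut-off raises sensitivity at the price of more false alarms, with no gain in the ability to tell patients apart. Two predictors can therefore be ranked on sensitivity only at the same specificity, or with both quantities in view.

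Here the device's cut-off is deliberately placed toward sensitivity. The surgeon's cut-off is whatever level of suspicion leads that surgeon to predict ileus, and nobody tunes it. If a yes/no call is all that is recorded, the surgeon contributes one point and the device a whole curve from which a favourable point is picked. Success would then show that the device flags more patients. It would not show that the device predicts ileus better than surgeons do, which is the conclusion a reader would draw.

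The same mismatch would affect AUC if someone calculated one for the surgeon. The AUC of a yes/no call is the average of its sensitivity and specificity, and this lies below the full-curve AUC of an equally good graded predictor.

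**Working it through.** The documents give no AUC, sensitivity, specificity, ileus rate, alpha or power, so there is no stated figure to reproduce. The values below are assumptions that show direction and size.

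**Model.** Equal-variance binormal: scores are normal with variance 1 and mean 0 without ileus, mean d with ileus. Device and surgeon share the same d, so they discriminate equally.

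- d = √2 × z(AUC). For AUC 0.80: 1.414 × 0.842 = 1.19.
- Sensitivity at a given specificity = Φ(d − z(specificity)).
- AUC of a yes/no call = (sensitivity + specificity)/2; at its best cut this equals Φ(d/2).

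**Step 1: the stated success rule.** For AUC 0.80 and a surgeon at specificity 0.90, sensitivity is Φ(1.19 − 1.28) = 0.464. For the device at specificity 0.70 it is Φ(1.19 − 0.52) = 0.747. Over a range of assumed AUCs:

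| Common AUC | Surgeon sensitivity at spec. 0.90 | Device at spec. 0.80 | Device at spec. 0.70 | Device at spec. 0.60 |
|---|---|---|---|---|
| 0.70 | 0.295 | 0.460 | 0.586 | 0.687 |
| 0.80 | 0.464 | 0.636 | 0.747 | 0.826 |
| 0.90 | 0.702 | 0.834 | 0.901 | 0.941 |

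In every row the device meets the rule although it discriminates no better. The result follows the relative cut-off. With AUC 0.80, a surgeon at specificity 0.70 and the device at 0.80, the device has 0.636 against 0.747 and fails, again with equal discrimination.

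**Step 2: what the extra sensitivity costs.** Take 100 patients and an assumed ileus rate of 20% (20 with ileus, 80 without), with AUC 0.80.

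- Surgeon at specificity 0.90: 20 × 0.464 = 9.3 cases detected; 80 × 0.10 = 8 false alarms.
- Device at specificity 0.70: 20 × 0.747 = 14.9 cases detected; 80 × 0.30 = 24 false alarms.

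The success rule counts the first quantity and ignores the second.

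**Step 3: AUC, only if one were computed for the surgeon from yes/no calls.** For a true AUC of 0.80:

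- Best cut: Φ(0.595) = 0.724; shortfall 0.80 − 0.724 = 0.076.
- Specificity 0.90: (0.464 + 0.90)/2 = 0.682; shortfall 0.80 − 0.682 = 0.118.

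Over true AUCs of 0.65 to 0.90 the shortfall is 0.043 to 0.082 at the best cut and 0.085 to 0.118 at specificity 0.90. In a simulation of 225 patients (20% ileus, both true AUCs 0.80, independent predictors, 2,000 runs per setting), the device's AUC exceeded the yes/no surgeon's in 93% of trials with the surgeon at specificity 0.70 and in 99% at 0.90. With a graded surgeon answer it did so in about half.

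**The case against.** **The device is not judged by AUC.** A reader might infer from the list of six measures, followed directly by the comparison with the surgeon, that device AUC will be set against surgeon AUC and that the result is biased. The documents do not support this. AUC is one of six device measures in the sentence on optimization, and no surgeon AUC, AUC test or AUC criterion is stated. Success is decided on sensitivity, which a yes/no call can supply. The shortfall in Step 3 needs both a yes/no call and a one-point AUC calculated from it, and the documents establish neither. This objection stands, and the AUC argument is limited accordingly.

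**The information is not lost for good.** A reader might also infer that yes/no collection rules out any fair comparison. It does not. Yes/no calls yield the surgeon's observed sensitivity and specificity, and device sensitivity can be read at that same specificity in the same patients. What cannot be recovered is the surgeon's performance at cut-offs the surgeon did not use.

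**A scale may exist.** Protocol Section XIII mentions case report forms, which are not among the documents, and one of them might hold a graded answer. If so, stating it in the SAP closes that part. It would not repair the success rule, because sensitivity alone with a movable threshold can be met by cut-off choice whatever scale the surgeon uses.

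**Specificity is mentioned.** The threshold is to keep specificity as high as possible. That is a guide for choosing the device's cut-off. It sets no floor, does not refer to the surgeon's specificity and is not part of the success rule, so it does not answer the point.

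**Conclusion.** The concern holds in this form: the plan compares a device whose threshold is chosen for sensitivity with a surgeon prediction of unstated format, and it declares success on higher sensitivity with no specificity condition. If the surgeon gives a yes/no call, equal discrimination is enough for the device to succeed whenever its cut-off is more lenient than the surgeon's. With AUC 0.80 for both and the surgeon at specificity 0.90, the apparent advantage is 0.17, 0.28 or 0.36 in sensitivity (0.636, 0.747 or 0.826 minus 0.464) at device specificity 0.80, 0.70 or 0.60.

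These sizes rest on the binormal model and the assumed AUC and specificities. The direction depends only on which predictor has the lower specificity. The surgeon's yes/no format is also an assumption. The AUC shortfall of about 0.08 to 0.12 would affect a descriptive contrast only, and only if a surgeon AUC were computed from yes/no calls.

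**What to change.** 1. **State the surgeon's response format** in the protocol and SAP, and add its collection to the schedule of events.
2. **Change the basis of the superiority conclusion.** Use the validation cohort, with the device threshold locked beforehand, and score device and surgeon in the same patients. Either compare sensitivity at matched specificity, reading the device's sensitivity at the surgeon's observed specificity, or report paired sensitivity and specificity together and require both to support the claim. If the matched reading is taken from the device's curve in the validation data, present it beside the result at the locked threshold, with an interval that allows for the surgeon's specificity being estimated.
3. **For patients still to be enrolled,** record the surgeon's probability of ileus (0–100%, or at least five ordered categories) at the same moment as the yes/no call. Compare AUCs as paired data only on graded answers.
4. **Where only a yes/no call exists,** report no surgeon AUC; plot the surgeon's point against the device curve.

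The cost is one extra field per patient and a short addition to the SAP. Patients already enrolled will have no graded answer unless one was collected. The protocol is dated September 2020 and its cover estimates complete enrolment by January 2020, so item 3 may reach few patients; items 2 and 4 need only the yes/no calls. The success claim may also be harder to meet.
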